7.6.4 Stopping Rule for Documented Severe Hypoglycemia

In the event of a first instance of documented severe hypoglycemia, dosing of a patient with study drug (ISIS 304801) will be suspended temporarily. The need to adjust the background medication and the suitability of the patient for continued dosing will be determined by the Investigator in (in consultation with the Sponsor Medical Monitor as needed). In the event of a second instance of documented severe hypoglycemia, after a re-challenge, dosing of a patient with study drug (ISIS 304801) will be stopped permanently.

7.7 Adjustment of Dose and/or Treatment Schedule

Dose adjustments for platelet count reduction must be made in accordance with Section 7.6.3 and Table (above).

Other dose adjustments, including dose interruptions, and/or decreasing the dose frequency will be allowed for safety or tolerability, after consultation with the Ionis Medical Advisor if possible. Dose adjustments should not occur unless absolutely necessary prior to the primary analysis time point (Week 12).

7.8 Withdrawal Criteria

1. **Withdrawal of consent.** A subject wishes to withdraw from the study as stated in the informed consent (all subjects reserve the right to withdraw from the study without prejudice).
2. **Adverse event (or SAE).** The patient develops laboratory test abnormalities that meet any of the stopping rules listed above, or any other adverse event that in the investigator's opinion necessitates withdrawal from the study.
3. **Investigator judgment.** An investigator feels it is in the subject's best interest to terminate participation. The detailed reasoning behind this decision will be documented.
4. **Pregnancy.**
5. **Ineligibility.** Includes study entry criteria violation.
6. **Significant Protocol Deviation.** Includes subject noncompliance or start of an unacceptable concomitant medication.

The reason for discontinuation of study treatment must be recorded in the electronic case report form (eCRF) and source documentation. All efforts will be made to complete and report the observations as thoroughly as possible up to the date of withdrawal. All information, including the reason for withdrawal from study, must be recorded in the eCRF.

Any patient who withdraws consent to participate in the study will be removed from further treatment and study observation immediately upon the date of request. These patients should be encouraged to complete the early termination study procedures and observations at the time of withdrawal. For patients withdrawn for reasons other than withdrawal of consent, every effort should be made to complete the early termination study procedures and observations at the time of withdrawal.

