4.1 Design/Randomization

This study has two components. Initially, subjects will receive ISIS 304801 or placebo, in a 1:1 randomized, double-blinded fashion for 16 weeks. Randomization will occur after verification that all eligibility criteria have been met. The randomization will be stratified by use of lipid-lowering medications. After completion of 16 weeks, all subjects will receive ISIS 304801 for 12 months in an open-label extension (OLE) phase. After discontinuation of ISIS 304801 (due to study end or any other reason) subjects will be followed for an additional 12 week withdrawal phase when possible. Patients who experience benefit (triglyceride lowering $\geq 50\%$) may receive an additional 12 months of open label drug (up to 24 months, total). This period may initiate immediately following the standard 12 month OLE, or following the withdrawal phase.

- 1° outcome (Δ in log₁₀ triglycerides):
 - C vs D
 - F vs G
- 2°/3° outcomes – within subject comparisons:
 - C vs E
 - F vs H
- Placebo vs drug comparisons
 - C vs H

1

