5.1 Sample Size Justification

The primary outcome variable is the change in log₁₀ fasting triglycerides from before treatment to 16 weeks of active drug treatment compared to placebo groups.

Preliminary data are available for 28 patients treated with ISIS 304801 and 24 treated with placebo. For the ISIS 304801 group, these data show a difference from baseline to follow-up of -423 (SD 400, 95% CI -578 to -268) mg/dL and -0.485 (SD 0.221, 95% CI -0.57 to -0.40) log₁₀ mg/dL. Converting the difference in log₁₀ mg/dL to a percent change [$100 \times (10^{-0.485} - 1)$] results in a percent change of -67% (95% CI -73% to -60%). For the placebo group, the absolute change is -12 (SD 406, 95% CI -12 to 184) mg/dL and -0.011 (SD 0.224, 95% CI -0.105 to 0.084) log₁₀ mg/dL. The percent change for the placebo group is -3% (95% CI -21% to 21%).

For comparison of placebo and ISIS 304801 we have chosen a SD of 0.25 log₁₀ mg/dL and a difference of 0.50 log₁₀ mg/dL. A trial with 5 patients in each group has 79% power to detect a difference of 0.50 log₁₀ mg/dL triglycerides in the change from baseline to follow-up between the ISIS and placebo groups, assuming a SD of 0.25 log₁₀ mg/dL and a two-sided significance level of 0.05.

Where preliminary data were available, sample size calculations were performed for secondary and tertiary study outcomes in addition to the primary outcome. The preliminary data and power estimates for a sample size of 10 subjects (using one-sample t-test for off versus on drug comparisons) are summarized in the table below. Based on these calculations, the study should be adequately powered to detect differences in total body insulin sensitivity, hepatic insulin sensitivity, fasting glucose, apoC-III serum level, HDL-C, VLDL-C, and apolipoprotein B48.

Based on these calculations, we plan to enroll a maximum of 20 patients, with a goal of 10 patients completing the study (defined as completing 16 weeks of active drug treatment). The accrual ceiling of 20 is planned because subjects will consent to the study prior to screening, thus we are accounting for up to 10 screen failures in the accrual ceiling.

	Outcome	Model	Treatment	Treat- ment Duration	Mean of Δ on-off drug (SD)	Power
Primary outcome	Absolute change log[serum triglycerides] (mg/dL)	High TG +/- diabetes and/or fibrate	ApoCIII ASO 300 mg/wk	16 wk	-0.48 (0.22)	>0.95
	% change serum triglycerides (%)	High TG +/- diabetes and/or fibrate	ApoCIII ASO 300 mg/wk	16 wk	-63 (20)	>0.95

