5.2 Statistical Methods for Data Analysis

Descriptive statistics such as mean and standard deviation (or median and interquartile range) will be used to summarize data in raw scale or change from baseline per visit.

The primary outcome, change in log₁₀ TG at Week 16 from baseline, and continuous secondary outcomes will be compared between ISIS 304801 and placebo groups using either two-sample t-test or Wilcoxon rank sum test as appropriate based on change from Baseline at Week 16. Changes from baseline based on tertiary/exploratory outcomes as well as change on log₁₀ TG at Week 16 will be examined using either one-sample t-test or Wilcoxon signed rank test as appropriate.

Repeated measures analysis of covariance using linear mixed models will be conducted in order to investigate trends on selected response variables and to compare active and placebo group while possible covariates are taken into account. There are three possible covariates: (1) Baseline level of the outcome of interest, (2) Baseline level of ApoCIII, and (3) Change in ApoCIII before and after the 16 week active drug intervention.

Inclusion of covariates will be checked using linear mixed models by checking Akaike Information Criteria (AIC) with inclusion of one covariate at a time

Analyses will include all available data even if patients do not adhere to their assigned treatments. Additional analyses will examine the effect of adherence to study results. We will also investigate the effect of missing data on the results using standard methods for missing data.

A p-value of 0.05 or less is considered significant.

6. Experimental Plan

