7.5 Safety Monitoring Rules

In addition to the standard monitoring of clinical safety parameters, the following guidelines are provided for the monitoring of selected parameters chosen based on preclinical and clinical observations. For the purposes of safety monitoring baseline is defined as the average of Day 1 pre-dose assessment and the last measurement prior to Day 1.

Confirmation Guidance: At any time during the Study (Treatment or Post-Treatment Periods), the initial clinical laboratory results meeting the safety monitoring criteria presented below **must be confirmed** by performing measurements (ideally in the same laboratory that performed the initial measurement) on new specimens. All new specimen collections should take place as soon as possible (ideally within 3 days of the initial collection). For stopping rules, if the initial laboratory result is observed during the Treatment Period, the results from the retest **must be available** prior to administering the next dose of Study Drug (ISIS 304801 or placebo).

Re-dosing Guidance: Patients with initial laboratory test values that reach a stopping rule must not be re-dosed until the re-test results are available. In general, patients who do not meet the stopping rules based upon retest may continue dosing. However, the Investigator will decide whether additional close monitoring of the patient is appropriate. If any of the stopping criteria described below are met below and are confirmed, the patient will be permanently discontinued from further treatment with Study Drug (ISIS 304801 or placebo), evaluated fully as outlined below and will be entered into the post-treatment evaluation portion of the study. Consultation will be conducted between the Investigator and the Ionis Medical Advisor as needed.

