7.6.2 Stopping Rules for Renal Function Test Results

In the event of persistent changes that are observed over 2 consecutive weeks, for **any** of the criteria below, dosing of a patient with Study Drug (ISIS 304801 or placebo) may be stopped temporarily:

1. Quantitative total urine protein measurement of > 3.5 g/24 hours
2. Estimated creatinine clearance calculated according to the formula of Cockcroft and Gault ≤ 40 mL/min that is confirmed by a 24 hour urine collection

The possible dosing re-initiation or follow-up schedule for any events meeting either of these criteria will be determined by the Investigator, in consultation with the Sponsor Medical Monitor as needed.

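### Section 7.8 does not separate stopping study drug from leaving the study, 7.5 and 7.6.2 prescribe different actions, and no section secures a Week 16 triglyceride value after an early stop

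*Combined protocol and SAP*

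**What the plan says.** All references are to the combined protocol and SAP.

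- **7.8, item 2** lists as a ground for withdrawal: "The patient develops laboratory test abnormalities that meet any of the stopping rules listed above". The same sentence goes on to other adverse events that, in the investigator's view, make leaving the study necessary.
- **7.5, re-dosing guidance**: once a stopping criterion is met and confirmed, "the patient will be permanently discontinued from further treatment with Study Drug (ISIS 304801 or placebo), evaluated fully as outlined below", and the patient then moves to post-treatment evaluation.
- **7.6.2 (renal)**: "dosing of a patient with Study Drug (ISIS 304801 or placebo) may be stopped temporarily", with a possible restart left to the investigator.
- **7.6.3 (platelets)**: some results lead to a permanent stop. A confirmed count below 75,000/mm³ without the specified bleeding leads to a suspension until recovery.
- **6.3.8**: patients who discontinue early are encouraged to attend a visit with the Week 80 assessments about 12 weeks after their last dose, or failing that to have a home nurse visit and telephone follow-up. 7.8 also seeks early-termination procedures at the time of withdrawal.
- **5.2**: the primary comparison is the change in log₁₀ TG at Week 16. "Analyses will include all available data even if patients do not adhere to their assigned treatments".

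**The concern.** One laboratory result can call for a pause, a permanent stop of drug with follow-up, or withdrawal, depending on which section the site reads. These are different actions for the patient, and they also produce different data.

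The principle in 5.2 works only if Week 16 is measured in patients who are off drug. If meeting a stopping rule ends participation, or moves the patient to a schedule timed from the last dose, there may be no Week 16 value to analyse. With five patients planned per arm, each missing value matters. If the reason for the loss is linked to the drug, the remaining comparison may also be biased.

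**Working it through.** **1. The instructions side by side**

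| Event | 7.5 | 7.6 | 7.8 item 2 |
|---|---|---|---|
| Confirmed liver criterion (7.6.1) | Permanent drug stop, follow-up | Permanent drug stop | Withdrawal criterion |
| Persistent renal criterion (7.6.2) | Permanent drug stop, follow-up | Temporary stop, restart possible | Withdrawal criterion |
| Platelets <75,000/mm³, no specified bleeding (7.6.3) | Permanent, if this counts as a stopping criterion | Temporary suspension | Withdrawal criterion, if this counts as a stopping rule |

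The renal row is a direct conflict: 7.6.2 is itself titled a stopping rule, so 7.5 and 7.8 both apply to it. The platelet row is arguable. In the liver row 7.5 and 7.6 agree, and only the meaning of 7.8 is open. Section 7.6.4 also pauses dosing after a first documented severe hypoglycemia, but that is a clinical event and may fall outside the laboratory wording of item 2.

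**2. Is Week 16 measured after an early stop?**

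The 7.8 procedures take place at withdrawal, so before Week 16 in the case at issue. The 6.3.8 visit falls at about (week of last dose + 12):

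- last dose Week 4: 4 + 12 = Week 16
- last dose Week 8: 8 + 12 = Week 20
- last dose Week 12: 12 + 12 = Week 24

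Only a last dose near Week 4 brings that visit close to Week 16, and then by coincidence. The post-treatment period to which 7.5 sends the patient is described in 6.3.7 as weekly home platelet checks for six weeks and one NIH visit at Week 80, which is 80 − 68 = 12 weeks after the end of dosing. No section retains a Week 16 visit for these patients.

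**3. Effect on precision**

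Inputs from 5.1: "we have chosen a SD of 0.25 log₁₀ mg/dL and a difference of 0.50 log₁₀ mg/dL"; "a two-sided significance level of 0.05"; "A trial with 5 patients in each group has 79% power". Allocation from 4.1: "in a 1:1 randomized, double-blinded fashion for 16 weeks". Section 5.1 gives no allowance for loss after randomization and attributes the ten places above the target to screen failures.

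Two-sample t-test power is P(|T| > t₀.₉₇₅,df), where T is noncentral t with df = n₁ + n₂ − 2 and noncentrality λ = δ / [σ√(1/n₁ + 1/n₂)] = 2 / √(1/n₁ + 1/n₂).

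| n₁ v n₂ | df | λ | Power |
|---|---|---|---|
| 5 v 5 (plan) | 8 | 2/√0.400 = 3.16 | 79.1% |
| 5 v 4 | 7 | 2/√0.450 = 2.98 | 72.5% |
| 5 v 3 | 6 | 2/√0.533 = 2.74 | 63.0% |
| 4 v 4 | 6 | 2/√0.500 = 2.83 | 65.7% |

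The first row reproduces the plan's 79%. A normal approximation gives 88.5%, so the plan used the t-test. One patient lost from one arm costs 79.1 − 72.5 = 6.6 percentage points with the rounded figures, and two cost 79.1 − 63.0 = 16.1.

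Section 5.2 also allows the Wilcoxon rank sum test. Simulated with exact p-values (20,000 runs, same difference and SD), its power is about 68% at 5 v 5, 60% at 5 v 4 and 51% at 5 v 3.

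These figures show lost precision only. They do not measure bias.

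**The case against.** A reader might infer that 7.8 plainly orders patients out of the study, and that Week 16 data will therefore be lost selectively from the active arm. The documents do not support that strength.

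- **Meaning of 7.8.** Its later text speaks of discontinuing study treatment, and it describes immediate removal from observation only for withdrawn consent. Pregnancy is on the same list, yet 7.4.1 withdraws a pregnant patient from drug and encourages follow-up. Section 6.2.2.5 says that missed doses do not remove a subject. Drug-only is a fair reading. This stands, but item 2 does use the language of leaving the study, so the text is ambiguous.
- **Platelet pause.** 7.6.3 calls it a suspension and keeps the term stopping criterion for permanent stops. This stands: the clear conflict is the renal one.
- **Selective loss.** 2.3.4 describes a mild platelet decrease associated with the drug. It recovered after treatment, without platelet-related adverse events. The same section reports no laboratory sign of a renal or hepatic effect. Unequal loss is plausible for platelets, has no documented basis for the renal rule, and is not shown for either.
- **Cause.** 7.8 is not the only source. After a permanent stop, 7.5 and 6.3.8 lead to the same gap however 7.8 is worded.
- **Replacement and other data.** The goal is 10 completers under a ceiling of 20, and no text forbids enrolling further. Replacement would limit the loss of power but would not remove bias. Section 5.2 also plans mixed models and unspecified standard missing-data methods. These use whatever was collected, but they do not supply a Week 16 measurement.

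**Conclusion.** The point holds as an internal inconsistency with a consequence for the primary endpoint. Three things are established from the text:

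- 7.8 item 2 leaves open whether a stopping rule ends dosing or participation.
- 7.5 and 7.6.2 give incompatible actions for a renal result, and 7.6.3 arguably adds a second such case.
- No section secures a Week 16 TG value for a patient permanently stopped before then.

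The loss is a risk, not a forecast. It requires a rule to be met before Week 16 and the sections to be applied as written. The documents give no expected frequency, and neither the direction nor the size of any bias can be derived from them. The power range of 73% (5 v 4) to 63% (5 v 3), against 79% planned, is illustrative. It assumes one or two patients lost from one arm, no replacement, the t-test, and the difference and SD in 5.1. The protocol should be amended on this point.

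**What to change.** 1. Reword 7.8 item 2 so that meeting a stopping rule concerns study drug only, and the patient stays in the study unless consent is withdrawn.
2. Amend 6.3.8, and the post-treatment wording in 7.5, so that patients who stop drug before Week 16 are still asked for the Week 16 assessment. At minimum this is a fasting TG sample, by home nurse visit if travel is not possible. State in 5.2 that this value enters the primary analysis.
3. Reconcile the temporary or permanent action among 7.5, 7.6.2, 7.6.3 and 7.8, and say whether the platelet suspension counts as a stopping rule. Which action is right is for the sponsor and investigator.

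Rewording 7.8 alone would not be enough: it would help patients whose dosing is only paused, but not those stopped permanently.

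The cost is amendment wording and one retained visit or blood draw for the few patients who stop early.

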6.2.2.5 Study Drug Administration

For each individual patient, Study Drug will be administered SC as a single 1.5 mL injection once weekly for Weeks 1-68. Self-administration will be allowed after appropriate training of the patient and/or caregiver. Patients should receive 1 dose per week, with weeks always defined relative to Study Day 1. For example, if a patient receives the first dose on a Monday, subsequent doses should be given on Mondays, if possible. If a patient misses an injection, or if dosing on the usual day is not possible, the patient can reschedule the injection provided that 2 doses are administered at least 2 days apart.

Every effort should be made to ensure the previous week's dose is given 7 days prior to a scheduled clinic visit. Subjects will not be removed from the study because of missed dosing; however, subjects missing more than 2 doses before Week 13 may not be evaluable for the primary endpoint.

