If none from the above-mentioned reason can be found, or if appropriate action fails to decrease FPG/HbA1c under the threshold values, rescue medication may be introduced at the investigator discretion and according to local guidelines.

Any patient who discontinues early from the placebo-controlled or OLE periods will be encouraged to attend a final in-person follow-up visit (Week 80 visit assessments per Appendix A) approximately 12 weeks after their last dose of Study Drug. If the patient declines or is unable to participate in the above, a home nurse visit for safety/efficacy labs.

If possible, an in-person visit for all assessments for primary and secondary efficacy and safety parameters planned in final primary endpoint assessment visit will be performed before adding the rescue medication. If an in-person visit cannot be conducted in a timely fashion, a home nurse visit for safety/efficacy labs will be attempted. If rescue medication is required, patients will continue the study treatment and remain in the study, although planned tests that will be affected by the use of rescue medication may be cancelled.

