7.9 Rationale for Subject Selection

The primary anticipated benefit of ISIS 304801 is TG reduction. The severity of hypertriglyceridemia in patients with lipodystrophy is quite variable. In this study, we are targeting the patient population to those with severe hypertriglyceridemia (>500 mg/dL) who are not only at increased risk for cardiovascular disease, but also at risk for acute pancreatitis. Patients with generalized lipodystrophy already have available a highly effective, approved therapy: leptin replacement. However, there are currently no approved therapies for patients with partial lipodystrophy. Hence, the population of partial lipodystrophy patients with severe hypertriglyceridemia has substantial unmet medical need, and has the greatest benefit to risk ratio from participation in this study. Based on our experience, we expect that the majority of subjects who enroll in this study will be female as females typically present with greater metabolic derangement. In addition, we anticipate that the majority of subjects will be Caucasian based on the demographics of partial lipodystrophy. Patients under 18 years of age are excluded as severe metabolic complications of partial lipodystrophy typically develop in adulthood, and there currently is no safety data for ISIS 304801 in children. Because there is a prospect for direct benefit, non-institutionalized adults who are unable to give informed consent but are considered able to comply with the study demands, will be eligible. If we enroll patients who are unable to provide their own consent, we will follow the procedures specified in NIH SOP 14E (“*Research Involving Adults Who Are or May Be Unable to Consent*”). If the study team has a concern that an adult patient may be unable to consent, the NIH Ability to Consent Assessment Team will be contacted to independently assess the subject’s ability to provide informed consent. If the NIH Ability to Consent Assessment Team (ACAT) determines that the subject is not able to consent, an appropriate surrogate (assessed by the NIH ACAT) will be assigned. Consent for research participation will then be obtained from either the surrogate or a legally authorized representative. Individuals designated as durable power of attorney (DPA) for health care or other valid advanced directive, or court-appointed guardians are accepted as legally authorized representatives. If after study enrollment, the patient is unable to comply with the protocol demands, they will be withdrawn from the protocol.

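### Withdrawal for noncompliance (7.8, 7.9) is not reconciled with 6.2.2.5 and 5.2, and no text secures a Week 16 triglyceride value afterwards, so non-adherent patients may be selectively lost from the primary comparison

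*Combined protocol and SAP*

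**What the plan says.** Four places in the combined protocol and SAP bear on what happens to a patient who does not adhere.

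- **Section 7.8, Withdrawal Criteria, item 6** is titled Significant Protocol Deviation and reads "Includes subject noncompliance or start of an unacceptable concomitant medication". The document does not define noncompliance or list which medications are unacceptable. On data, the section says "All efforts will be made to complete and report the observations as thoroughly as possible up to the date of withdrawal", with early-termination procedures at the time of withdrawal. It speaks of discontinuing study treatment and of withdrawing from the study without separating the two.
- **Section 7.9, Rationale for Subject Selection** says: "If after study enrollment, the patient is unable to comply with the protocol demands, they will be withdrawn from the protocol".
- **Section 6.2.2.5, Study Drug Administration** says "Subjects will not be removed from the study because of missed dosing", and in the same sentence that "subjects missing more than 2 doses before Week 13 may not be evaluable for the primary endpoint".
- **Section 5.2, Statistical Methods** says "Analyses will include all available data even if patients do not adhere to their assigned treatments". It also promises additional analyses of the effect of adherence and of missing data.

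Section 6.3.8 encourages a patient who stops early to attend a visit with the Week 80 assessments about 12 weeks after the last dose. The fallback is a home nurse visit.

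**The concern.** Section 5.2 sets out an analysis of patients as randomised, whatever their adherence. That analysis needs a Week 16 fasting triglyceride value from patients who did not adhere. Sections 7.8 and 7.9 allow those patients to be taken out of the study before the value exists, and 6.2.2.5 allows them to be set aside even if they stay.

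Noncompliance happens after randomisation and can depend on the arm. Section 2.3.4 reports injection-site reactions as the most frequent adverse events of the drug, and lack of effect could discourage patients on placebo. If such patients leave, the groups left at Week 16 are no longer the groups that were randomised. With about five patients per arm, one or two removals can change the make-up of an arm, and missing-data methods have little to work with.

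**Working it through.** **1. Who may be removed.** Take a blinded-period patient who has missed several doses. Under 6.2.2.5 the missed doses do not remove the patient. Under 7.8, item 6, the patient can be withdrawn if the missed doses are judged to be significant noncompliance, and no threshold says when they are. Under 7.9 a patient unable to comply is withdrawn. If the patient stays and has missed more than two doses before Week 13, 6.2.2.5 still leaves it open whether the patient counts for the primary endpoint, while 5.2 would include the patient. Two investigators could apply the text differently to the same case.

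**2. What is measured after withdrawal.** Section 7.8 asks for procedures when the patient withdraws, which is before Week 16 for anyone withdrawn earlier in the blinded period. Section 6.3.8 places its visit about 12 weeks after the last dose:

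- last dose in Week 4: 4 + 12 = Week 16, which matches by coincidence;
- last dose in Week 10: 10 + 12 = Week 22;
- last dose in Week 14: 14 + 12 = Week 26.

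So neither section secures a Week 16 value.

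**3. The plan's power, reproduced.** Inputs from Section 5.1: 5 per arm, difference 0.50, SD 0.25 log10 mg/dL, two-sided 0.05. For a two-sample t-test, the noncentrality is difference / (SD × √(1/n1 + 1/n2)) = 0.50 / (0.25 × √0.4) = 3.162 on 8 degrees of freedom. The noncentral t gives 79.05%, matching the stated 79%. With missing Week 16 values that are not replaced:

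- 5 v 4: noncentrality 0.50 / (0.25 × √0.45) = 2.981, 7 df, power 72.5%;
- 4 v 4: 0.50 / (0.25 × √0.5) = 2.828, 6 df, power 65.7%;
- 5 v 3: 0.50 / (0.25 × √0.5333) = 2.739, 6 df, power 63.0%.

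**4. Why power is not the argument.** Suppose that one of the five active patients is kept but has no drug effect (an assumption). Simulating 200,000 trials with the plan's inputs gives power of about 46%, and about 22% if two of five are kept on those terms. Losing that one patient instead leaves 5 v 4 and 72.5%. On this assumption, keeping non-adherent patients lowers power.

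**5. What is at stake is the quantity estimated.** On the same assumption, and with no other difference between adherers and non-adherers:

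- one of five: all randomised, (4 × 0.50 + 1 × 0) / 5 = 0.40; adherers only, 0.50;
- two of five: all randomised, (3 × 0.50 + 2 × 0) / 5 = 0.30; adherers only, 0.50.

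As reductions relative to placebo, 1 − 10^(−0.50) = 68%, 1 − 10^(−0.40) = 60% and 1 − 10^(−0.30) = 50%. Section 5.2 points to the all-randomised figure. Selective removal would deliver the adherers' figure.

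**The case against.** The strongest reply is that the sections can be read together. Item 6 is limited to significant deviations, and 6.2.2.5 is a specific rule for one kind of deviation. Noncompliance could then mean other duties, such as contraception, diet or platelet monitoring. The sentence in 7.9 closes a paragraph on adults who cannot give their own consent and might be meant only for them. This reading is possible, but the text does not state it. Missed doses are the most obvious form of noncompliance, and nothing in 7.8 excludes them.

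A reader might infer a further contradiction with Section 7.5.8, which says of patients given glycaemic rescue that "patients will continue the study treatment and remain in the study". The documents do not support that as it stands. Rescue is permitted there, so a clash arises only if a permitted drug also counts as unacceptable. Section 7.5.8 also seeks the endpoint assessments before rescue, where possible.

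A reader might also infer that the Week 16 data are certain to be lost and that the primary analysis becomes one of adherers. That goes too far. A withdrawal after Week 16 costs no primary value, the procedures in 7.8 and 6.3.8 yield some data, and the mixed models in 5.2 could use earlier values. The number of interim triglyceride values could not be counted from the text of Appendix A available here.

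Finally, the enrolment ceiling of 20 might allow replacement. Section 5.1 assigns that margin to screen failures, however, and sets its goal in completers, so replacement would tend to favour adherent patients.

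**Conclusion.** The point holds as a risk of selection bias created by unreconciled text. Sections 7.8 and 7.9 permit removal for noncompliance, 6.2.2.5 bars it for missed doses but leaves evaluability open, 5.2 assumes that the data exist, and no section secures a Week 16 triglyceride value after a withdrawal in the blinded period. The loss is possible, not certain.

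Its size cannot be derived, because the documents give no rate of withdrawal or non-adherence. The shifts from 0.50 to 0.40 or 0.30 illustrate one or two patients of five with no drug effect.

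It is tempting to rest the case on the fall in power from 79% to between 63% and 73%. Those figures are correct for one or two unreplaced losses, but they do not support a change, since retention may lower power further. The reason to act is that the comparison in 5.2 should be of the patients as randomised.

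**What to change.** Reconcile 7.8, 7.9, 6.2.2.5 and 6.3.8 with 5.2:

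- In 7.8, separate stopping study drug from leaving the study. Define noncompliance and unacceptable concomitant medication, and record both as protocol deviations.
- State in 7.8 and 6.3.8 that these patients are still asked to have the Week 16 fasting triglyceride and other endpoint assessments unless they withdraw consent. Say whom the sentence in 7.9 covers, and bring it into line.
- State in 5.2 that they are included in the primary analysis as randomised, and limit the evaluability wording in 6.2.2.5 to a supportive analysis.

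Decisions on study drug and on removal for safety stay with the investigator.

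The cost is a few sentences across five sections. The Week 16 inpatient visit is already in Appendix A. The downside is that keeping patients who are off drug may dilute the observed effect and lower power, as shown in the working. The supportive analysis can show the result in adherent patients alongside.
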